5.0 STUDY DESIGN & METHODS

50 patients will be recruited over 12-18 months. Half of the patients will receive the Medacta GMK Sphere prosthesis (Ball-and-socket), while the other half will receive the Medacta GMK posterior stabilized prosthesis (Cam-and-post). Patients will be randomized in the operating room through the opening of opaque, study-numbered envelopes prior to skin incision.

Patient-reported outcomes will be administered pre-operatively, immediately post-operatively, 6 weeks post-operatively, 3 months post-operatively, 6 months post-operatively, 12 months post-operatively, and 2 years post-operatively. Patient-reported outcomes will be measured using the Oxford knee score (see appendix 1), Knee Society Score, VR-12 (see appendix 2), the Forgotten Joint Score (FJS) for the knee (see appendix 3), and the Kujala Scoring Questionnaire (see appendix 4) as well as the physical function, pain interference, and pain behavior PROMIS CATs (see appendix 5). These questionnaires will be completed at the routine post-operative clinic visits or over the phone through PROMIS Assessment Center. The Forgotten Joint Score (FJS) will only be administered at the subject's 12 month post-operative time point and the Kujala Scoring Questionnaire will only be administered at the subject's 2 year post-operative time point.

At 3-6 months post-op, the operative knee will be examined by a single Sports Orthopaedics attending surgeon [name], who is an expert in assessing knee stability. The attending will grade the stability of the knee in various degrees of flexion according to section 4 of the International Knee Documentation Committee's Knee Ligament Standard Evaluation Form (see appendix 3). KT1000 arthrometer (MEDmetrics, San Diego, CA) measurements will also be taken by a single provider at the 3-month postoperative visit. The patient will also be graded on the get-up-and-go test at this time.

A prospective chart review will be performed starting at the time of enrollment and ending at the study completion date to obtain and verify the following data from NMH Medical records (PRIMES, Cerner PowerChart) and NMFF Medical Records (EpicCare, IDX/GE Centricity):

- EPIC Number
- MRN
- Medical History
- Medications
- Surgical History
- Date of Surgery
- Time taken to complete surgery
- Type of implant

- Post operative quality of prosthesis position/fixation
- Pre and post-operative lab values (Hg, plts, WBC, ESR, CRP, INR, etc)
- Complications/Reoperations

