
APPENDICES**1. Oxford Knee Score**

During the past 4 weeks..					✓ tick one box for every question
During the past 4 weeks.....					
1	How would you describe the pain you usually have from your knee?				
	None	Very mild	Mild	Moderate	Severe
					
2	During the past 4 weeks..... Have you had any trouble with washing and drying yourself (all over) because of your knee ?				
	No trouble at all	Very little trouble	Moderate trouble	Extreme difficulty	Impossible to do
					
3	During the past 4 weeks..... Have you had any trouble getting in and out of a car or using public transport because of your knee ? (whichever you would tend to use)				
	No trouble at all	Very little trouble	Moderate trouble	Extreme difficulty	Impossible to do
					
4	During the past 4 weeks..... For how long have you been able to walk before pain from your knee becomes severe? (with or without a stick)				
	No pain/ More than 30 minutes	16 to 30 minutes	5 to 15 minutes	Around the house only	Not at all - pain severe when walking
					
5	During the past 4 weeks..... After a meal (sat at a table), how painful has it been for you to stand up from a chair because of your knee ?				
	Not at all painful	Slightly painful	Moderately painful	Very painful	Unbearable
					
6	During the past 4 weeks..... Have you been limping when walking, because of your knee ?				
	Rarely/never	Sometimes, or just at first	Often, not just at first	Most of the time	All of the time
					

1. Oxford Knee Score (Cont.)

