During the past 4 weeks... *✓ tick one box for every question*

During the past 4 weeks.....					
7	Could you kneel down and get up again afterwards?				
	Yes, Easily	With little difficulty	With moderate difficulty	With extreme difficulty	No, Impossible
					
During the past 4 weeks.....					
8	Have you been troubled by pain from your knee in bed at night?				
	No nights	Only 1 or 2 nights	Some nights	Most nights	Every night
					
During the past 4 weeks.....					
9	How much has pain from your knee interfered with your usual work (including housework)?				
	Not at all	A little bit	Moderately	Greatly	Totally
					
During the past 4 weeks.....					
10	Have you felt that your knee might suddenly 'give way' or let you down?				
	Rarely/ never	Sometimes, or just at first	Often, not just at first	Most of the time	All of the time
					
During the past 4 weeks.....					
11	Could you do the household shopping on your own ?				
	Yes, Easily	With little difficulty	With moderate difficulty	With extreme difficulty	No, Impossible
					
During the past 4 weeks.....					
12	Could you walk down one flight of stairs?				
	Yes, Easily	With little difficulty	With moderate difficulty	With extreme difficulty	No, Impossible
					

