2. VR-12

Instructions: This questionnaire asks for your views about your health. This information will help keep track of how you feel and how well you are able to do your usual activities.

Answer every question by marking the answer as indicated. If you are unsure how to answer a question, please give the best answer you can.

(Circle one number on each line)

1. In general, would you say your health is:

EXCELLENT	VERY GOOD	GOOD	FAIR	POOR
1	2	3	4	5

2. The following questions are about activities you might do during a typical day. Does **your health now limit you** in these activities? If so, how much?

YES,
LIMITED
A LOT YES,
LIMITED
A LITTLE NO,
NOT
LIMITED
AT ALL

a. **Moderate activities**, such as moving a table, pushing a vacuum cleaner, bowling, or playing golf?

1 2 3

b. Climbing **several** flights of stairs?

1 2 3

3. During the past 4 weeks, have you had any of the following problems with your work or other regular daily activities **as a result of your physical health**?

NO, NONE OF THE TIME	YES, A LITTLE OF THE TIME	YES, SOME OF THE TIME	YES, MOST OF THE TIME	YES, ALL OF THE TIME
-------------------------------	------------------------------------	--------------------------------	--------------------------------	-------------------------------

a. **Accomplished less** than you would like.

1 2 3 4 5

b. Were limited in the **kind** of work or other activities.

1 2 3 4 5

4. During the past 4 weeks, have you had any of the following problems with your work or other regular daily activities **as a result of any emotional problems** (such as feeling depressed or anxious)?

NO, NONE OF THE TIME	YES, A LITTLE OF THE TIME	YES, SOME OF THE TIME	YES, MOST OF THE TIME	YES, ALL OF THE TIME
-------------------------------	------------------------------------	--------------------------------	--------------------------------	-------------------------------

a. **Accomplished less** than you would like.

1 2 3 4 5

b. Didn't do work or other activities as **carefully** as usual.

1 2 3 4 5

5. During the past 4 weeks, how much did pain interfere with your normal work (including both work outside the home and house work)?

NOT AT ALL	A LITTLE BIT	MODERATELY	QUITE A BIT	EXTREMELY
1	2	3	4	5

These questions are about how you feel and how things have been with you during the past 4 weeks. For each question, please give the one answer that comes closest to the way you have been feeling.

6. How much of the time during the past 4 weeks:

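### At the immediate post-operative visit, the four-week recall of the Oxford Knee Score and most VR-12 items falls mainly before surgery, yet these scores are not excluded from between-arm tests

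*Combined protocol and SAP*

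**What the plan says.** Section 5.0 (Study Design & Methods) sets one schedule for the patient-reported outcomes: "Patient-reported outcomes will be administered pre-operatively, immediately post-operatively, 6 weeks post-operatively, 3 months post-operatively", then 6 months, 12 months and 2 years. It names the instruments: "Patient-reported outcomes will be measured using the Oxford knee score (see appendix 1), Knee Society Score, VR-12 (see appendix 2"), followed by the Forgotten Joint Score, the Kujala questionnaire and three PROMIS CATs.

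Two instruments are taken off the common schedule. For one, "The Forgotten Joint Score (FJS) will only be administered at the subject's 12 month post-operative time point"; the Kujala questionnaire is likewise confined to 2 years. Oxford and VR-12 carry no such limit, so they are due at every listed visit, including the immediate one.

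On setting, the section says: "These questionnaires will be completed at the routine post-operative clinic visits or over the phone through PROMIS Assessment Center". It gives no day or window for the immediate visit.

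In Appendix 1, every Oxford item carries the stem "During the past 4 weeks". Appendix 2 uses the same recall for most of the VR-12, for example "3. During the past 4 weeks, have you had any of the following problems with your work or other regular daily activities" and "During the past 4 weeks, how much did pain interfere with your normal work". Neither appendix changes the stem for an early visit.

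Section 6.0 (Statistical Plan) compares the two cohorts with a t test or Mann-Whitney U test for continuous variables and a chi-square or Fisher's exact test for categorical ones, at p < 0.05. It names no primary time point, excludes no visit, and does not say how the immediate scores are to be used.

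**The concern.** A questionnaire that looks back four weeks, completed shortly after the operation, asks mostly about a time when the study implant was not in place. Some Oxford items make this plain. "Could you kneel down and get up again afterwards" and the questions on household shopping and stairs would largely be answered from experience of the arthritic knee. The same holds for the Oxford item on the knee giving way, which is one of the few patient-reported items that bears directly on stability, the subject of the trial.

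The VR-12 has a further difficulty at this visit. Its items on activity limits ask about the present, while most of the others look back four weeks. One form would mix the patient's state just after surgery with recall of the weeks before it.

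If these scores are labelled post-operative and tested between arms, a significant difference would more likely be chance than an implant effect, and a null result could be misread as early equivalence.

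**Working it through.** The plan gives no figure on this point, so there is none to reproduce. The check compares recall windows with visit timing.

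**Inputs**
- Recall window: four weeks, that is 28 days (Appendices 1 and 2).
- Visits: immediate, then 6 weeks and later (section 5.0).
- Day of the immediate visit: not stated. Days 0 to 14 are shown as an assumed range, with days 0 to 3 as the plain reading of the word.

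**Step 1: which items carry the four-week stem**
- Oxford: items 1 to 12, so 12 of 12.
- VR-12: items 3a, 3b, 4a, 4b, 5, 6a, 6b, 6c and 7, so 2 + 2 + 1 + 3 + 1 = 9. There are 12 health items (1, 2a-b, 3a-b, 4a-b, 5, 6a-c, 7), and 9/12 = 75%.
- VR-12 without that stem: item 1 (general health), items 2a-b (current limits), and items 8 and 9 (change from one year ago). Counting these last two, 9 of the 14 printed items have four-week recall.

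**Step 2: share of the window that lies before surgery**

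For a form completed on post-operative day d, the share is max(0, 28 − d)/28.

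| Day of completion | Days before surgery | Share |
|---|---|---|
| 0 | 28 of 28 | 100% |
| 3 | 25 of 28 | 89% |
| 7 | 21 of 28 | 75% |
| 14 | 14 of 28 | 50% |
| 28 | 0 of 28 | 0% |
| 42 (6 weeks) | 0 of 28 | 0% |

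**Step 3: first clean visit**

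The share reaches zero at day 28. The first scheduled visit after that is 6 weeks, where the window covers roughly days 14 to 42 and is wholly post-operative.

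**Step 4: what the analysis does with the scores**

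The tests in section 6.0 apply to the measures obtained from each group. Nothing there sets the immediate Oxford or VR-12 scores apart from later ones.

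These shares count calendar days. They are not shares of the score, because patients may give recent days more weight than the stem asks.

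**The case against.** The strongest reply is that little hangs on this. The trial's objective is knee stability, and the objective measures (the ligament examination and the KT1000) are taken between 3 and 6 months. Randomised arms share the same recall problem, so neither implant is favoured. No visit from 6 weeks on is touched. The lack of a primary endpoint and of multiplicity control in section 6.0 is a larger problem, and fixing it would remove much of the chance-finding risk described here. All of this stands, and it limits the weight of the point. It does not make the early scores measures of the new knee.

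A second reply is that the visit is undefined. Completion at a clinic visit or by telephone leaves room for a date a week or two after surgery. This also stands, and it is why the range to day 14 is shown. Even at day 14, half the window precedes the implant.

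A reader might infer more than the documents support:
- **That everything collected at this visit describes the pre-operative knee.** The VR-12 measures general health, and items 1 and 2a-b are not four-week items. The recall periods of the Knee Society Score and the PROMIS CATs are not in the text, so nothing is shown for them.
- **That a comparison at this visit cannot detect any difference at all.** That would require an effect of exactly zero. Unless the form is completed on the day of surgery, part of the window is post-operative, so the supported statement is that it can show little.
- **That the early scores dilute a post-operative average or distort a longitudinal model.** Section 6.0 plans neither.

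**Conclusion.** The point holds as a validity problem at one visit. As written, the immediate Oxford score and 9 of the 12 VR-12 health items refer mainly to the time before surgery: 89% to 100% of the window if the forms are completed on days 0 to 3, falling to 75% at day 7 and 50% at day 14. Mainly is therefore right for any date before day 14; at day 14 the split is even. The timings are assumed because the plan gives none, and the shares take patients to answer over the period the stem names.

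Scores of this kind can show little implant effect, and the plan leaves them open to between-arm testing. There is no directional bias, and later visits are sound. With no primary time point named, any effect on the trial's main conclusion cannot be quantified. The change is worth making because it is simple, not because the trial's result depends on it.

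**What to change.** In section 5.0, start the post-operative Oxford and VR-12 series at 6 weeks and keep the pre-operative assessment as it is. The section already sets instrument-specific visits for the Forgotten Joint Score and the Kujala questionnaire, so one more sentence of the same kind is enough.

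If the forms are still wanted at the early visit, define that visit in days. State in section 6.0 that Oxford and VR-12 scores from it are descriptive only and excluded from between-arm tests.

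The cost is one line in the schedule or one in the statistical plan. The first option also eases the questionnaire burden, which section 5.0 lists among the risks, though only in part because other instruments remain at that visit. The small loss is that the general and current-state VR-12 items (1 and 2a-b) would not be collected there, or under the second option would not be tested. The Knee Society Score and PROMIS CATs need no change on this ground, but their recall periods should be checked against the early visit in the same way.

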Stability of the Medial Pivot Total Knee Prosthesis

PRINCIPAL INVESTIGATOR:

[name]
Department of Orthopaedic Surgery
[name]
[name]

SUB-INVESTIGATORS:

[name]
University of Chicago

[name]
Northwestern University

[name]
Northwestern University

[name]
Northwestern University

[name]
Northwestern University

PARTICIPATING SITES:

Northwestern Memorial Hospital

Synopsis

Title	Stability of the Medial Pivot Total Knee Prosthesis
Short Title	Medial Pivot Knee Stability
Protocol Date	04/08/2016
Study Duration	2 years
Study Center(s)	Northwestern Memorial Hospital, Northwestern Memorial Faculty Foundation, Northwestern University
Objectives	To compare objective and subjective measures of knee stability following total knee arthroplasty with a medial pivot design vs. a posterior stabilized design
Number of Subjects	100 (50 in each group)
Diagnosis and Main Inclusion Criteria	Patients requiring total knee arthroplasty that present to Northwestern Memorial Hospital or to [name] or [name] clinic

TABLE OF CONTENTS

Synopsis.....
1.0 Introduction.....
2.0 Study Objectives.....

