7.0 DATA COLLECTION & RECORD KEEPING

All information regarding the nature of the proposed investigation provided to the investigator (with the exception of information required by law or regulations to be disclosed to the IRB, the subject, or the appropriate regulatory authority) will be kept in confidence by the principal investigator. All personal information will be treated as strictly confidential and not made publicly available. All records will be stored in a locked filing cabinet and password-protected computers which are accessed only by the Principal Investigator, co-investigators, and authorized study staff. All identifiable data will be destroyed one year after the study is complete.

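### Does a Synopsis study duration of 2 years conflict with 12 to 18 months of recruitment followed by 2-year follow-up?

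*Combined protocol and SAP*

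**What the plan says.** The Synopsis has one line on length, "Study Duration 2 years", and does not say whether it means the whole study or each patient's participation.

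Section 5.0 gives the working schedule. On recruitment it says "50 patients will be recruited over 12-18 months". Its last two patient-reported assessments are at "12 months post-operatively, and 2 years post-operatively". One instrument is confined to the final time point: the "Kujala Scoring Questionnaire will only be administered at the subject's 2 year post-operative time point". The Forgotten Joint Score is given only at 12 months. The stability examination is at 3 to 6 months after surgery, and the arthrometer measurement is at the 3-month visit.

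Two other provisions depend on when the study ends. Chart review in Section 5.0, which includes complications and reoperations, runs "starting at the time of enrollment and ending at the study completion date". Section 7.0 says "All identifiable data will be destroyed one year after the study is complete". Neither section defines completion by a date or an event.

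**The concern.** If the Synopsis line is the total length of the study, it leaves no time to recruit, because follow-up alone takes 24 months. A study closed at month 24 would lose the only Kujala assessment for essentially every patient and could lose some of the 12-month Forgotten Joint Scores.

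The undefined completion date looks like a second weakness. If chart review stops on one calendar date for everyone, early patients are observed for complications and reoperations longer than late ones. Section 6.0 offers only chi-square or Fisher's exact tests for categorical variables, with no allowance for time at risk. The date on which identifiable data must be destroyed also cannot be read from the document.

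**Working it through.** **Inputs.** Stated duration: 24 months (Synopsis). Recruitment period A: 12 to 18 months for 50 patients (Section 5.0). Last assessment: 24 months after surgery (Section 5.0). Delay from completion to destruction of identifiers: 12 months (Section 7.0). Surgery is assumed to follow enrollment at once, and accrual is assumed uniform.

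**1. The plan's own figure.** Follow-up per patient runs from surgery to the last assessment, which is 24 months. This reproduces the Synopsis entry exactly.

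**2. The entry read as a total.** Total = A + 24.
- A = 12: 12 + 24 = 36 months.
- A = 18: 18 + 24 = 42 months.
- Excess over the stated figure: 36 − 24 = 12 months, and 42 − 24 = 18 months.

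The entry therefore fits one reading and not the other. The 36 to 42 months is a minimum for 50 patients. The Synopsis gives the number of subjects as "100 (50 in each group"), which is a separate discrepancy and would lengthen recruitment. It does not affect which reading of the 2 years fits.

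**3. What closure at month 24 would cost.** The share of patients reaching a visit at v months would be max(0, min(A, 24 − v)) / A.

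| Visit | A = 12 | A = 18 |
|---|---|---|
| 6 months | 12/12 = 100% | 18/18 = 100% |
| 12 months | 12/12 = 100% | 12/18 = 67% |
| 24 months | 0/12 = 0% | 0/18 = 0% |

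These losses need someone to stop the study at month 24. No section says to do so, and Section 5.0 ties the Kujala assessment to each subject's own 2-year point. Even on this reading, the 3-to-6-month stability measures would be complete.

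**4. Length of chart review under a common end date.**
- Completion at month 24: 24 months for the first patient and 24 − A = 12 or 6 for the last.
- Completion at the last 2-year visit: A + 24 = 36 or 42 months for the first patient and 24 for the last.

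The spread is A, that is 12 to 18 months, in both cases. If completion were taken subject by subject, the spread would be zero.

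**5. Destruction date.**
- Completion at month 24: 24 + 12 = month 36.
- Completion at the last 2-year visit: 36 + 12 = month 48, to 42 + 12 = month 54.

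With A = 18, only (36 − 24)/18 = 67% of patients would have had their 2-year visit by month 36, and the last such visit would fall at month 42. A study with scheduled visits outstanding is not complete in any ordinary sense, so the month-24 definition defeats itself.

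**The case for a change.** The strongest argument for a change is that the document never says which reading of the 2 years applies. On the reading that works, the field is mislabelled and no total duration appears anywhere. An ethics board or data manager could take the line literally. The missing definition of completion matters separately: under a common end date, a crude proportion with a complication or reoperation refers to no fixed period and cannot be reported as a 2-year rate. The remedy is cheap, since a few words would settle the labels and a 24-month window after each patient's surgery would make the proportion interpretable.

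The wording criticism stands: the label is ambiguous and completion is undefined. The consequences do not follow from it. The operative schedule is in Section 5.0, and it is clear and feasible. Unequal chart-review time affects how a crude rate is described. It is not expected to bias the comparison of prostheses, because patients are randomized and calendar time of entry is balanced between arms in expectation. Section 6.0 does not single out an analysis of complications over the whole chart-review period. If completion is the last 2-year visit, every patient has at least 24 months of review, apart from dropout, so analysts can still report over a common period if they wish. Making a 24-month window mandatory would discard later reoperations that had been observed. A censored time-to-event analysis is an equally respectable answer, and statisticians may reasonably differ on the choice.

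**Conclusion.** No change to the plan follows. The Synopsis entry is best read as follow-up per patient, where it agrees with Section 5.0 to the month. As a total it would fall 12 to 18 months short of the 36 to 42 months needed, but nothing in the document applies it that way. Completion is a missing detail that a sensible team would fill with the last patient's 2-year visit, which puts destruction of identifiers at months 48 to 54. The 12-to-18-month spread in chart review arises only under a common end date and is not expected to favor either arm.

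This rests on three assumptions: the team follows the Section 5.0 schedule, surgery follows enrollment without material delay, and recruitment of 50 patients takes the stated 12 to 18 months. Longer recruitment or a delay before surgery would lengthen the calendar but would not alter the conclusion. No outcome, test or between-arm comparison depends on the Synopsis line.

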- Knee pathology: Date of onset, age of onset, any associated injuries, radiographic findings, dates and types of prior therapeutic interventions and their effectiveness.
- Physical exam: Specifically, the following information will be obtained: documentation of nerve function, strength, sensation, vascular status, pre-operative stability.
- Outcome data at final follow-up: Ambulatory aid use, orthosis use, job change as result of knee pathology, whether patient went back to work if applicable.

All data collected from chart review will be coded and noted on the Data Collection Form. All patient collected chart data as well as the PROMIS surveys will be coded. The data points will be identified by a random string of five numbers and letters that will be assigned by the PROMIS online database system.

Potential risks involved in this study include the inconvenience of completing questionnaires and stability testing, pain during stability testing, or a fall during the get up and go test. The patient's level of pain will be assessed on the visual analog scale prior to stability testing, and if the degree of pain is felt to be too great by the subject or examiner, the test will be deferred. Inquiry as to the patient's usual level of function will inform the appropriateness of the get up and go test. If the patient does not normally perform transfers into/out of chairs, then those analyses will be deferred. Any ambulation aids that the patient is accustomed to using will be made available.

One possible risk related to the patient's participation in this study is the loss of privacy. To reduce these risks, all of the information collected will be coded (the patient will be assigned a study number and all data will be linked to that number and not the patient's name) and stored in a password-protected file on a password-protected computer. Some of the questions asked may be upsetting, or the patient may feel uncomfortable answering them. If the patient does not wish to answer a question, they may skip it and go to the next question.

Additionally, both knee prostheses included in this study are in common use by orthopaedic surgeons today. Therefore, there are no additional risks involved in the use of these implants for this study.

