6.0 STATISTICAL PLAN

This proposed sample size is small enough to feasibly recruit over the given time period, yet large enough to correlate differences between the two groups.

Data Cleaning and Crosschecking:

Data cleaning and crosschecking will be conducted prior to analyses. These procedures will include: 1) Comparing patient counts with accrual records; 2) Grouping data by assessment and ensuring a match with the designated number of assessments; 3) Cross-checking baseline and follow-up assessment dates; 4) Ensuring correct questionnaire count match to electronic data fields; 5) Summarizing missing data and checking for definable patterns.

Statistical Analysis:

This study has the primary objective of comparing outcome measures between the MP and PS knee prostheses. We will calculate descriptive statistics for the patient characteristics and measures obtained from each group (means, SD, range). We will use the Shapiro-Wilk test to identify whether each continuous variable fits a normal distribution. We will then use a two-tailed Student's t test for parametric data or the Mann-Whitney U test for nonparametric data to compare the two cohorts. The Pearson χ^2 or Fischer's exact test will be used for categorical variables where appropriate. The level of significance will be defined at $p < 0.05$.

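### Section 5.0 states no safeguard that keeps the IKDC section 4 examiner or the KT1000 provider masked to the implant

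*Combined protocol and SAP*

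**What the plan says.** Section 2.0 sets the goal as a comparison of subjective and objective knee stability between the medial pivot and posterior stabilized designs. Section 5.0 then describes three clinic-based assessments.

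- **IKDC section 4, at 3-6 months:** "the operative knee will be examined by a single Sports Orthopaedics attending surgeon", described as an expert in judging stability. "The attending will grade the stability of the knee in various degrees of flexion according to section 4" of the form in Appendix 3.
- **KT1000 arthrometer:** "measurements will also be taken by a single provider at the 3-month postoperative visit".
- **Get-up-and-go:** "The patient will also be graded on the get-up-and-go test at this time". No grader is stated.

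Three other statements in Section 5.0 bear on who might know the implant.

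- **Allocation:** "Patients will be randomized in the operating room through the opening of opaque, study-numbered envelopes prior to skin incision".
- **Chart review:** the items taken from the medical records include "Type of implant".
- **Coding:** "the patient will be assigned a study number and all data will be linked to that number", given as a protection against loss of privacy.

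Section 6.0 compares the arms with a t test or the "Mann-Whitney U test for nonparametric data to compare the two cohorts", and with chi-square or Fisher tests for categorical variables. No section mentions blinding or masking of assessors or patients.

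**The concern.** The IKDC grades are a clinician's judgement by hand. In section 4 of the Appendix 3 form, most items have four levels, such as millimetre bands for joint opening or negative, glide, clunk and gross for pivot shift. A borderline knee can fall either side of a boundary, and an assessor who knows the implant may place it, without intending to, according to what they expect of that design. KT1000 is an instrument reading, but a person takes it, so the question arises there too.

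If such a shift differed by arm, it would appear in the results as a difference in stability between the implants. Having one examiner per measure helps consistency and is not a flaw. It does not settle the matter, because one person's expectation would run through every knee in both arms.

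**Working it through.** **1. Does any text mask the assessors?** The plan has no figure to reproduce here, so the check is a reading of each statement that might supply masking.

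| Statement (Section 5.0) | What it secures | Does it cover the 3-month and 3-6 month assessments? |
|---|---|---|
| Opaque envelopes opened in the operating room | Concealment until assignment | No; it ends when the envelope is opened |
| Study number in place of the name | Privacy | No; it hides the patient's identity in the data, not the implant |
| One examiner, one provider | Consistency between patients | No; it does not address what that person knows |
| Implant type taken from the medical records | Data capture | No; it shows the information is on file, and no text limits the assessors' access to it |

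The sentences describing the two assessments read as complete around the removed name, so redaction of that name does not account for the missing statement.

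**2. Can the analysis repair a shift?** Let the observed difference in means be the true difference plus b, where b is the arm-related assessor shift. The t test sees only the sum. The Mann-Whitney, chi-square and Fisher tests likewise see only the recorded values or grades. None has information with which to separate the two parts.

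**3. How large could the effect be?** The documents give no value for b, so it is assumed and a range is shown. The outcome is KT1000, treated as continuous, with no true difference.

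Inputs:
- two-sided 5% level (Section 6.0);
- n = 50/2 = 25 per arm from the Section 5.0 total, or 50 per arm from the Synopsis;
- b in SD units, assumed to be a uniform shift in one arm.

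Formula: the rejection probability of the two-sample t test under a noncentral t distribution with df = 2n − 2 and noncentrality b × √(n/2).

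Example at b = 0.2:
- 25 per arm: df = 48, noncentrality 0.2 × √12.5 = 0.707, rejection probability 10.7%;
- 50 per arm: df = 98, noncentrality 0.2 × √25 = 1.0, rejection probability 16.8%.

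| Assumed shift b (SD) | 25 per arm | 50 per arm |
|---|---|---|
| 0 | 5.0% | 5.0% |
| 0.05 | 5.3% | 5.7% |
| 0.1 | 6.4% | 7.9% |
| 0.2 | 10.7% | 16.8% |
| 0.3 | 18.0% | 31.8% |

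A simulation of 200,000 trials at b = 0.2 gave 10.6% and 16.7%, in agreement. No such table is offered for the IKDC grades, because the answer would depend on an assumed split across grades and on the test chosen. None is offered for get-up-and-go.

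**The case against.** The strongest reply is that silence is not a defect in conduct. Assessor names and consent pages are removed from the public text, so whether the examiner overlaps with the operating surgeons cannot be checked. Sending the examination to a sports orthopaedics attending may already separate it from the surgical team. Listing implant type as a chart-review item shows that study staff collect it, not that the examiner reads it. All of this stands. A reader might infer that the assessors will know the implant, or that the trial is unmasked; the documents support neither. They support only the statement that no safeguard is written down.

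The second reply concerns size. The figures are for KT1000, the more instrument-based measure, and rest wholly on an assumed shift. At 0.05 SD they are almost nominal. The introduction also reports conflicting literature, so no common direction of expectation is established. This stands too: the table shows how the mechanism works and is not an estimate of bias in this trial.

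Third, the get-up-and-go sentence directly follows the KT1000 sentence, so the same provider may be meant. That is possible but not stated. It is a point of clarification, not the core of the concern. Nor do the documents rank that test below the others.

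Finally, masking may be imperfect if the examiner can feel the design. That limits the benefit for the IKDC grades, but it is no reason to leave records, radiographs and conversation open as sources.

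**Conclusion.** The concern holds in a limited form. The plan states no safeguard that masks the IKDC section 4 examiner or the KT1000 provider at assessment, and its other provisions do not supply one. It does not follow that they are unmasked. Followed as written, the plan leaves the hand-graded part of the objective stability comparison open to a bias that its analysis cannot detect or remove.

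The size is unknown. The illustrative KT1000 range, 6-18% at 25 per arm and 8-32% at 50 per arm, assumes a uniform shift of 0.1 to 0.3 SD and no true difference, and should carry no weight beyond illustration. The case rests on the text and on two readings of it: that IKDC section 4 and KT1000 are the objective measures meant in Section 2.0, and that the removed pages contain no masking rule for assessors. The change should be made because it is cheap and protects a central comparison. Confidence is medium, since masking may already be practice.

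**What to change.** Add to Section 5.0 that the IKDC examiner and KT1000 provider already planned, and whoever grades get-up-and-go (whose role should be stated):

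- did not take part in that patient's operation;
- are not told the allocation;
- do not view the operative note, implant record or postoperative radiographs before recording their results.

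Also ask patients not to discuss their implant at these assessments, and report as unmasked any assessment where these conditions could not be met. The rule for deferring a test because of pain needs no change.

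The cost is protocol wording and minor clinic logistics at visits already planned, with no extra staff. Masking may remain incomplete if the design can be felt on examination, and the report should say so. If these safeguards are already in use, stating them lets readers credit them.
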